9. RISKS

a. Potential Risks

i. Investigational devices

N/A

ii. Investigational drugs

N/A

iii. Commercially available drugs, biologics, reagents or chemicals

N/A

iv. Procedures

Data Collection: Self-reported survey will be kept confidential and collected online via secure RedCap database system. There are no known psychological risks to subjects completing self-report subjective rating scales or participating in the intervention sessions. However, the survey and intervention may contain items or questions that make the subjects feel uncomfortable in that they ask about their physical and psychological health and feelings/emotions. Subjects will be informed that any items on questionnaires or topics discussed in the intervention modules that produce these effects may be skipped or ignored.

Protections Against Risk. All research staff have completed rigorous training in the protection of human subjects, including CITI training. The plan for protecting privacy and confidentiality recognizes that the protection of privacy in studies involving sensitive data is of utmost importance. We will attempt to do this in several ways. The research assistant will introduce the study to eligible participants and explain the purposes, benefits, and risks of the project to the subjects, and offer them an opportunity to ask questions and/or decline participation. The voluntary and confidential nature of the

research, as well as limits to confidentiality, will be highlighted during informed consent process. Study participation will not interfere with clinical care and all patients have standard access to the treatment team on a routine (clinical care) and emergency basis. All responses to interview items will be given by subjects in private. Survey data collection will only occur through tools and resources that have acceptable security features. We will minimize all communications that involve names or other identifying information. All clinically-relevant and study information will be kept in locked files in locked offices or password protected files

All recordings of intervention sessions will be saved on a password-protected secure server. Information about subjects will not be accessible to any non-authorized study personnel without the written consent of the subject. In all datasets we will use ID numbers only. A separate dataset linking names with ID numbers will be accessible only to authorized study personnel under the direction of the PI.

There's a small chance there will be some discomfort upon pricking their finger and collecting their HbA1c levels if they have never done one before. Sometimes the discomfort can last a day or two but often is mild and goes away. If the discomfort persists, we will ask them to contact us.

v. Radioisotopes/radiation-producing machines

N/A

vi. Physical well-being

There is a chance of some discomfort upon having their blood drawn and collecting their HbA1c levels if they have never done one before. Sometimes the discomfort can last a day or two but often is mild and goes away. If the discomfort persists, we will ask them to contact us.

vii. Psychological well-being

Psychological discomfort may result from some of the questions in the questionnaires, but participants may choose not to answer questions if they feel uncomfortable. Additionally, participants may feel uncomfortable sharing in the group setting. If they feel uncomfortable, they will be able to communicate with the group leaders, RA, or principal investigator to express feelings of discomfort and hopefully be comforted. In past trials Project Health, participants have not reported discomfort discussing sensitive materials in group sessions.

viii. Economic well-being

N/A

ix. Social well-being

N/A

x. Overall evaluation of risk

Minimal risk.

b. International Research Risk Procedures

N/A

c. Procedures to Minimize Risk

Confidentiality: All materials, such as questionnaires and data collected from each participant will be identified by an ID number in order to ensure confidentiality. Additionally, all researchers will have a thorough understanding of the participants' rights to confidentiality.

Emotional discomfort: Participants will be reminded of their right not to answer specific questions during the research visit. Research assistants will be sensitive to signs of exhaustion or other distress and will schedule breaks or will end the visit as warranted to protect the comfort of participants. All participants will receive information about whom to contact if they have lingering questions, concerns, or distress regarding any aspect of the study.

Beck Depression Inventory: The Beck Depression Inventory will be included as one of our study surveys. Once this survey is filled out by a participant, the study team will check all responses, specifically question #9 that addresses suicidal ideation. If anything above a "0" is answered, the study team will follow appropriate procedures and talk with the participant. The study team has undergone crisis management training and been given a crisis protocol sheet that includes questions to assess the severity of the suicidal ideation with the participant. This protocol contains a resourcing tool and steps that the participant can take if future suicidal ideation occurs. We will also provide a counseling referral list with contacts in the Palo Alto area.

All research staff have completed and will maintain rigorous training in the protection of human subjects, including CITI training. The plan for protecting privacy and confidentiality recognizes that the protection of privacy in studies involving sensitive data is of utmost importance. We will attempt to do this in several ways. Research staff will introduce the study to eligible participants and explain the purposes, benefits, and risks of the project to the subjects, and offer them an opportunity to ask questions and/or decline participation. The voluntary and confidential nature of the research, as well as limits to confidentiality, will be highlighted during informed consent process. Study participation will not interfere with clinical care and all patients have standard access to the treatment team on a routine (clinical care) and emergency basis. Survey data collection will only occur through tools and resources that have acceptable security features. We will minimize all communications that involve names or other identifying information. All clinically-relevant and study information will be kept in locked files in locked offices or password protected files.

All recordings of intervention sessions will be saved on a password-protected secure server. Information about subjects will not be accessible to any nonauthorized study personnel without the written consent of the subject. In all datasets we will use ID

numbers only. A separate dataset linking names with ID numbers will be accessible only to authorized study personnel under the direction of the PI.

d. Study Conclusion

If the subject wants to end their participation in the study at any time, they can do so. If the investigator determines that participation would be harmful to the subject or investigator in any way, they can terminate the experiment. If not ended early, participate participation will end after the 3-month follow-up.

e. Data Safety Monitoring Plan (DSMC)

i. Data and/or events subject to review

N/A

ii. Person(s) responsible for Data and Safety Monitoring

N/A

iii. Frequency of DSMB meetings

N/A

iv. Specific triggers or stopping rules

N/A

v. DSMB Reporting

N/A

vi. Will the Protocol Director be the only monitoring entity? (Y/N)

Yes

vii. Will a board, committee, or safety monitor be responsible for study monitoring? (Y/N)

No

f. Risks to Special Populations

N/A

10. BENEFITS

Participants, in both the Project Health groups and the educational control, may experience a reduction in weight gain and an improvement in glycemic control. Thus, we anticipate that participants will show improvements in both mental and physical health, but that improvements will be greater for intervention verses educational control participants. If the Project Health is found to be effective there is justification to test it on a larger scale and hopefully implement it broadly among this high-risk population.

11. PRIVACY AND CONFIDENTIALITY

Health information including height and weight information, medical diagnosis, date of diagnosis, A1c levels, psychological and behavioral measurements (surveys), and demographic information such as age, gender, ethnicity, and psychological history. We will also obtain names and contact information (phone number and email) for study coordination purposes, but this information will be securely kept separate from research data and only accessed by research staff. We will not disclose this information to others.

All patient information will be strictly confidential and protected health information will not be released to those outside of the research study. The only information that will be released will be de-identified information reported at the group (not individual) level so that individual information will not be identifiable in any way. After obtaining electronic consent for study participation, all participants will be assigned a unique identification number that will be used for all study documentation. A list of participant names and unique identifiers will be kept in a password-protected database on a secure server accessible only by the PI and trained research staff. The list will be destroyed after publication of study findings. All information a password-protected computer. Other Stanford University's Lucile Packard Children's Hospital staff may become aware of an individual's study participation; however, hospital regulations require that all healthcare providers treat medical records information confidentially. All recordings of intervention sessions will be saved on a password protected secure server. Information about subjects will not be accessible to any non-authorized study personnel without the written consent of the subject. In all datasets we will use ID numbers only. A separate dataset linking names with ID numbers will be accessible only to authorized study personnel under the direction of the PI.

The Research Participation team will create an Honest Broker Export file based on the inclusion/exclusion criteria entered by the study team in the STARR Cohort Discovery Tool. The following information will be used to create the Honest Broker export file: name, age, address, diagnosis, gender, contact information. Only after patients (identified via STARR and invited via honest broker) express interest in the study will the study teams use Epic to help obtain contact information as to set up a time for the initial phone screening.

The following information from Epic will be required to confirm inclusion/exclusion criteria: name, age, address, diagnosis, gender, contact information. Only after patients (identified via STARR and invited via honest broker) express interest in the study will study teams use Epic to help confirm inclusion/exclusion criteria. The PHI accessed will be the minimum necessary to determine eligibility.

Evaluating a Type 2 Diabetes Prevention Program

NCT: 5822648

04/16/2023

**Analyses.** For the continuous response variables in Aims 1 and 2 we will fit linear mixed effects models (LME) or generalized additive models (GAM) if change across the study is nonlinear. All models will include an interaction of time since the start of the study (in months) and condition (as well as all lower-order main effects). For both LMEs and GAMs, we will control for the lack of independence between the observations within a participant by including random intercepts and random slopes (if necessary) for the participants in our models and for participants nested within groups.

To detect for differences in the onset of T2D (Aim 1) between the intervention and control condition, we will fit a Cox proportional hazard model using the survival package (Therneau, 2022) in R. The proportional hazard assumption will be assessed and in the event of violations of this assumption, stratified proportional hazard models will be fit.

For the mediation analysis for Aim 2, the mediation package (Tingley et al., 2014) in R will be used to employ the causal mediation approach described in Imai et al. (2010). This is a more general and flexible causal mediation framework than the traditional structural equation modeling approach to mediation. Specifically, this approach enables (1) definitions of causal mediation effects that are independent of a particular statistical model, (2) specification of the identifiability assumption, and (3) a framework that can be applied to a myriad of models (most importantly for this study, LMEs, GAMs, and survival models). In addition, sensitivity analyses can be conducted to explore the sequential ignorability assumption. Using this framework involves modeling the onset of T2D via a parametric survival regression model that includes condition and the proposed mediator (percent body fat). This model's output is then combined with the mediator model's output, the percent body fat model from Aim 1, and used to calculate the average causal mediation effect (ACME), the proportion of the total effect that is mediated as well as other mediation statistics, which can then be tested using either quasi-Bayesian Monte Carlo or the non-parametric bootstrap.

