1. PURPOSE OF THE STUDY

a. Brief Summary

This study aims to test the effectiveness of a Type 2 Diabetes (T2D) prevention program for individuals who have been diagnosed with prediabetes compared to a T2D educational control group. Project Health is an obesity prevention program and has produced a 42% to 53% reduction in future onset of overweight/obesity and also produced greater reductions in negative affect compared to assessment-only controls that persisted. Project Health has been adapted to prevent onset of T2D among individuals with prediabetes. The study aims to test the effectiveness of Project Health at reducing BMI, HbA1c levels, increase physical activity and improve glucose control.

b. Objectives

Aim 1 is to test the hypothesis that participants who complete the T2D Project Health will show significantly greater reductions in BMI and HbA1c, the primary outcomes, by 3-month follow-up than participants randomized to the T2D education video control condition.

Aim 2 is to test the hypothesis that participants who complete the T2D Project Health will show significantly greater reductions in self-reported caloric intake and greater increases in physical activity by 3-month follow-up than participants randomized to the T2D education video control condition.

If this pilot and feasibility trial provides evidence that Project Health significantly reduces weight gain and improves glucose control, we plan on conducting a fully-power trial that will test whether this brief, cost effective prevention program significantly reduces future onset of T2D among individuals with impaired glucose control. As such, this represents a translational study on the prevention of T2D.

c. Rationale for Research in Humans

The purpose of this study is to test the effectiveness of a Type 2 Diabetes prevention program, adapted Project Health. This study must use humans due to the nature of the educational aspect because the programs require speech as a method of communication.

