If participants are randomized to Project Health, they will meet in groups of 6 individuals led by clinician. Groups will meet once a week in-person for an hour, for six weeks. Each week involves homework that participants are asked to complete before the next session. If participants are assigned to the Education intervention, they will be asked to watch one-hour of videos including information about T2D each week for six weeks.

Post-Test:

After the six weeks of either Project Health or the educational control, participants will be asked to complete the same assessments that they did at baseline, but not the blood tests.

3-Month Follow-up:

At 3-month follow-up, participants will again complete the assessments. After the 3-month follow-up, participants have completed all study responsibilities.

1-Year Follow-Up:

We propose to collect A1c data over 1 year follow up

First we will check to see in Epic if the participant is a Stanford patient.

If they haven't had a recent test or not in Stanford system we will ask if they would be willing to send any recent A1c blood test results.

If no to both, the participant will be offered to have an HbA1c kit sent to them to do a finger prick at home. The participant will send the kit to the research lab in Minnesota to be processed. Kits come with already pre-paid shipping labels that are addressed only to the Minnesota lab, no return address or any PHI from the participant is included. The participant will be offered a \$10 Amazon gift card for completing and shipping the HbA1c kit.

b. Procedure Risks

These research procedures provide minimal risk to subjects. We are using current and empirically evaluated measures and research staff available who have been fully trained both in administrating physiological interviews. Project Health has also been tested in

multiple trials and has produced only positive effects, there has been no history of symptoms worsening as a result of participating in the program.

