The above procedures present minimal risk. Engaging in the intervention modules carries minimal risk for emotional discomfort or stress. Subjects will have the option of not participating in conversations or exercises in the intervention modules that cause them any discomfort. They will also be free to withdraw from participating in the intervention and/or overall study at any time. Survey measures are non-invasive and present minimal risk. Using blood draws for A1c may be minimally invasive but provide no added level of risk or discomfort beyond routine diabetes management tasks.

c. Use of Deception in the Study

Deception will not be used.

d. Use of Audio and Video Recordings

Participants will be informed that we will make video recordings of Project Health groups for clinical supervision and quality assurance purposes. These recordings will be reviewed by the primary investigator to assess intervention fidelity and therapeutic competence of the group leaders. Email supervision based on these ratings will be provided to facilitators which has been found to maximize intervention effects. After they are viewed and rated for fidelity and competence, all records of the recordings will be deleted from devices and destroyed. Recordings are not optional. As the group sessions are in-person it is possible for someone to go out of view of the camera, but their voices will still be recorded. There are three main factors that increase cognitive dissonance: public accountability, level of effort, and voluntary basis. By recording the sessions, public accountability is greatly increased, and the effect of the intervention improves. Thus, if they are in Project Health individuals must be willing to be recorded.

e. Alternative Procedures or Courses of Treatment

There are not any programs designed to decrease risk of T2D.

f. Will it be possible to continue the more (most) appropriate therapy for the participant(s) after the conclusion of the study?

If Project Health produces significantly larger improvements than the educational lectures, we will offer the Project Health to educational controls.

g. Study Endpoint(s)

It is important to test whether effects persist at 3-month follow-up even if there are good effects at posttest, as it is possible that the effects may not persist. The effects of this brief prevention program typically have shown good persistence through 3- year follow-ups.

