As a part of the informed consent process, subjects will be asked if they are participating in any other research projects. Their participation in other protocols will not exclude them from participation in this study.

k. Payments to Participants

Participants will be eligible to earn up to \$150 for completion of all study activities. \$25 will be awarded per completion of each assessment and blood testing (pre-test, post-test, 3-month) and then an additional \$25 if all assessments are completed. With a \$10 gift card for 1-year follow-up.

- (1) baseline = \$25
- (2) baseline blood tests = \$25
- (3) post-test = \$25
- (4) 3 month follow-up = \$25
- (5) 3-month follow-up blood test = \$25
- (6) completion of all the previous five = \$25
- (7) 1-year follow-up blood test = \$10 Amazon gift card

l. Costs to Participants

There will be no cost to participants.

m. Planned Duration of the Study

It is estimated that the study will take one year. The screening is expected to take 10-15 minutes. Active participation will last about 4 months. Participants will complete the baseline assessment (1.5 hours) and collect HbA1c levels, then complete the six-week intervention (each session is one hour), and then a post-test assessment (about 1.5 hours) and HbA1c. After the initial baseline assessment and the post-test, participants will have completed all necessary tasks until the 3-month follow-up where they will complete the same tasks as the baseline and post-test assessments. While the groups are running, data analysis on baseline data will begin. Once we have complete data for posttest and 3-month follow-up, we will conduct data analysis on the outcome measures. We propose to collect A1c data over 1 year follow up.

First we will check to see in Epic if the participant is a Stanford patient. If they haven't had a recent test or not in Stanford system we will ask if they would be willing to send any recent A1c blood test results. If no to both, the participant will be offered to have an HbA1c kit sent to them to do a finger prick at home and send it to a lab in Minnesota to be processed.

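### The primary analysis is not tied to the 3-month contrast in Aim 1, and the switch from a straight line to a GAM has no stated criterion

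*SAP*

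**What the plan says.** Protocol section 1b states the Aim 1 hypothesis: Project Health participants "will show significantly greater reductions in BMI and HbA1c, the primary outcomes, by 3-month follow-up" than controls. The same section makes the result the gate to a larger study: "If this pilot and feasibility trial provides evidence that Project Health significantly reduces weight gain and improves glucose control", a fully powered trial is to follow.

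The SAP (Analyses) proposes linear mixed models, or "generalized additive models (GAM) if change across the study is nonlinear". On the condition effect it says "All models will include an interaction of time since the start of the study (in months) and condition", with lower-order terms. It also allows "random slopes (if necessary) for the participants in our models and for participants nested within groups". It does not mention the 3-month visit, does not say which coefficient or contrast tests Aim 1, and gives no test, threshold or decision time for nonlinearity.

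On timing, protocol section 2a puts post-test after the six-week programme and then a 3-month follow-up, without saying whether the three months run from baseline or from post-test. Section 8m says "Active participation will last about 4 months". On HbA1c, section 2a says that at post-test "participants will be asked to complete the same assessments that they did at baseline, but not the blood tests", whereas section 8m lists HbA1c at post-test and the itemised payments in section 8k list no post-test blood test. Sections 2a and 8m also plan a 1-year HbA1c; the SAP does not say whether it enters the model.

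**The concern.** A months-by-condition coefficient is a difference in rate of change averaged over all visits. Aim 1 asks for a difference in change at one visit. The two agree in some schedules and effect shapes and not in others, and the documents do not fix which applies. The schedule matters because month 4 to 4.5 makes the visits unequally spaced. The shape matters because section 2g says "The effects of this brief prevention program typically have shown good persistence", so an effect that appears by post-test and then holds is a case to plan for.

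The GAM switch could repair a poor straight line, but the SAP does not say when it is triggered or which GAM contrast is then the test. That leaves the analyst a choice of primary test after seeing the data, in a trial whose result decides whether a larger one is run.

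**Working it through.** **Inputs.** From the documents: 62 participants expected (section 8a), allocation with 50% probability to each arm (section 2a), a six-week programme (1.5 months), and active participation of about 4 months (section 8m). The documents give no alpha, SD, effect size or power, so there is no sample size calculation to reproduce. Assumed: 31 per arm, two-sided 5%, BMI at all three visits, complete data, equal correlation r between visits, no group-level variation in change.

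**Step 1: what the straight line estimates for BMI.** For visits t = 0, 1.5, T, the fitted slope times T puts weight w = T(t − mean t)/Σ(t − mean t)² on each visit. For T = 4, the mean is 1.833 and the sum of squares 8.167, so w = (−0.898, −0.163, 1.061). An effect reached at post-test and held has pattern (0, 1, 1), giving −0.163 + 1.061 = 0.898. The 3-month contrast uses (−1, 0, 1) and gives 1.

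**Step 2: power if the line is always kept.** Relative noncentrality is the recovered fraction divided by √(Σw²/2). The effect is set so that the unadjusted 3-month contrast has 80% power (noncentral t, 60 df, noncentrality 2.847; 0.72 SD at r = 0.5, 0.32 SD at r = 0.9). Neither arm comparison is adjusted for baseline.

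| Visits (months) | Weights | Held effect recovered | Relative noncentrality | Equivalent N = 62 × square | Power |
|---|---|---|---|---|---|
| 0/1.5/3 | −1, 0, 1 | 100% | 1.000 | 62 | 80% |
| 0/1.5/4 | −0.898, −0.163, 1.061 | 90% | 0.907 | 51 | 72% |
| 0/1.5/4.5 | −0.857, −0.214, 1.071 | 86% | 0.873 | 47 | 69% |

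These power figures do not depend on r. With equal spacing, or with an effect that grows linearly, the line and the contrast estimate the same quantity.

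**Step 3: power under the SAP's switch.** Three readings of nonlinear were tried, with a flat control arm. Whenever the flag fires, the GAM analysis is assumed to report the 3-month contrast; the SAP does not say so.

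| Trigger | Flagged, T = 4 | Power, T = 4 | Flagged, T = 4.5 | Power, T = 4.5 |
|---|---|---|---|---|
| 5% test of between-arm curvature | 52% | 78% | 56% | 77% |
| AIC on that term | 73% | 79% | 77% | 79% |
| 5% test within Project Health arm | 80% | 79% | 84% | 79% |

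The line is kept in 16% to 48% of trials, depending on the reading, and the loss is about 1 to 3 points (powers simulated, 100,000 trials per schedule).

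**Step 4: HbA1c.** With baseline and one follow-up value, slope times T equals the change contrast, so there is no bias. Curvature cannot be assessed, and a random slope cannot be separated from residual error. With a post-test value added, HbA1c behaves like BMI. With the 1-year value in a straight-line model (t = 0, T, 12), the recovered fraction of a held effect is:
- T = 3: mean 5, sum of squares 78; 3 × (−2 + 7)/78 = 0.19.
- T = 4.5: mean 5.5, sum of squares 73.5; 4.5 × (−1 + 6.5)/73.5 = 0.34.

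**Step 5: baseline adjustment.** Adjusting the change contrast for baseline multiplies its variance by (1 − r²)/(2(1 − r)) = (1 + r)/2: 0.75 at r = 0.5 and 0.95 at r = 0.9, with r assumed.

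**The case against.** The strongest reply is that the SAP already provides for nonlinearity, so figures for an always-kept line describe a procedure it does not propose. This stands. A reader might infer from Step 2 that the trial gives up 8 to 11 points of power, or that 62 participants act like 47 to 51. The documents do not support that as the expected loss. A pooled 5% curvature test would do somewhat worse than the three triggers shown (76% at T = 4, 75% at T = 4.5). However, section 10 expects that both arms may improve. If controls show a held change half the size of the between-arm effect, the pooled and Project Health-arm tests flag about 98-99% of trials, and power returns to about 80%.

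The timing and shape are also inferred. About 4 months suggests counting from post-test but does not settle it. Any lag between baseline and the first group session moves post-test later: visits at 0/2/5 recover 92% of a held effect, 0/2.5/5.5 recover 97%, and 0/2/4 recover 100%. If only 75% of the effect is present at post-test, the line recovers 94% (T = 4) or 91% (T = 4.5). Section 2g itself warns that effects may not persist. All this bears on size. It does not supply the missing contrast or criterion.

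A reader might also infer that the problem is confined to BMI. That holds only if HbA1c has two in-study values and the 1-year value stays out of the model, and the documents establish neither. Nor does the lack of a baseline covariate bias the comparison: the model already compares change from baseline, so only precision is lost.

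**Conclusion.** The omission is certain from the text: no 3-month contrast is named, and the rule that picks the model has no criterion. The numerical cost is conditional. For BMI it requires three measured visits, unequal spacing, an early held effect and a retained line. Under the switch, with the GAM assumed to report the right contrast, the loss is about 1 to 3 points of power for the three triggers examined, and slower onset or a lag before post-test reduces it further. The larger exposure is HbA1c if the 1-year value enters a straight line; whether it would is not stated.

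The point should be fixed because the primary test is otherwise chosen after the trajectories are seen and the remedy costs almost nothing. It does not show that the planned analysis is invalid.

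**What to change.** In the SAP:
- Name the difference between arms in change from baseline at the 3-month visit as the primary test for BMI and for HbA1c.
- Estimate it with visit as a category and a common baseline mean across arms, or by ANCOVA on baseline where an outcome has only two visits. Keep the group random effect.
- Do not use the LME/GAM switch in the primary test, nor random slopes for two-visit outcomes. With three visits, visit as a category already allows any mean pattern.
- Keep the 1-year HbA1c out of the 3-month contrast, or enter it as its own visit category.

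In the protocol:
- State whether the three months run from baseline or from post-test.
- Reconcile sections 2a, 8k and 8m on post-test HbA1c.

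No new data are needed. The baseline part is a precision gain (variance 25% lower at r = 0.5, 5% lower at r = 0.9), not a bias correction. The cost is a few more parameters and no single rate-of-change summary. If the effect truly grew linearly, the unadjusted contrast would have 2% to 4% more variance than the line (variance ratios Σw²/2 of 0.98 at T = 4 and 0.96 at T = 4.5).
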